4.6 Data Collection

Data processing, statistical analysis and publication of the data material will be performed by a PhD student (coordinating investigator) together with health professionals (primary and secondary investigators) from the participating pulmonary medical outpatient clinics. The randomized trial started with the inclusion of participants 05JUL2021, and the last participant is expected to be

included by 31AUG2025. Data collection ceases 31AUG2026, and the project is scheduled to run until 31AUG2026.

A nurse will be responsible for collecting baseline data, performing lung function measurement, weight and height at baseline and the 12-month follow-up as well as performing blood sampling and questionnaires at three-, six- and nine-month follow-ups, according to Fig. 2. Data will be obtained via the electronic health record. Medical decisions are made by doctors only. Proper handling, storage, and delivery of medication and the primary daily project management is handled by the coordinating investigator. Recruitment, medical examinations, and distribution and accounting of medication will be assisted by primary investigators at each centre.

The data collected will be treated confidentially and only by personnel associated with the project. This includes demographic data, health status, current illnesses, medications, medicinal side effects, hospital admissions, and results from various examinations during the trial. Data will be reported in Electronic Case Report Forms (eCRF) specific for each participant. The data is encrypted, stored in online servers and protected by the Data Protection Authority through various security precautions. The physical copies of the CRF are kept in locked archives on the involved departments for 5 years.

Data in eCRF will be handled by the investigator at each centre and in accordance with the Law for Data Protection and the Danish Law for Privacy Regulation.

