5.1 Primary Endpoints

ICS and Azithromycin

The primary outcome targets admissions and death within 365 days of randomization. This is assessed in the following analysis:

- Number of hospitalization-requiring COPD exacerbations and/or death within 365 days (continuous data: analysis with chi squared test)

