Events will be considered exclusively within the trial period, encompassing participant enrollment from screening to the last visit day. An annual safety report (ASR) of all SARs and SUSARs occurring during the trial period along with a description of the rules of registration and reporting of adverse events as given in this protocol will be submitted to the Clinical Trials Information System (CTIS). All SAEs, SARs, SUSARs will be reported in the final report to the CTIS at the conclusion of the trial.

7. Exclusion from or interruption of the trial

Participants may at any time terminate the study if the physician responsible for the study deems it necessary with medical justification (allergy to the medicine, safety risk, or other adverse circumstances). The investigator can furthermore at all hours unblind the Azithromycin/placebo treatment by contacting Glostrup Apotek. Termination and unblinding should preferably be done in agreement with the coordinating investigator of the project. The participant in question will be informed immediately of health concerns, project termination, and future treatment plan. Additionally, participants may, at any time, withdraw their informed consent. This will not have any consequence on further treatment.

8. Economy

The initiative for the trial was taken by the steering committee of COP:TRIN (Chronic Obstructive Pulmonary Disease: Trial Network) and the departments of pulmonary medicine at Gentofte Hospital, Herlev Hospital, Hvidovre Hospital, Bispebjerg Hospital, North Zealand Hospital, and Aalborg Hospital. The project budget is approximately DKK 7.433.600. This amount will cover salary to researchers, supervisors, nurses and auxiliary staff, the cost of data collection, equipment, medication, laboratory analyses, diagnostic tests, and potential hospitalizations.

Funding has been sought from various foundations, including Region H Research Fund. The Scientific Ethics Committee and the trial participants will be informed of the sponsors, their financial contribution and its part in the project, and information on grant recipient (Whether the support is paid directly to the investigators or their department/institute).

The Novo Nordisk Foundation has supported the initiative with 4.6 million DKK by a grant to [name].

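### Section 7 names leaving the study as the only response to a drug reaction or safety concern, and gives no route for collecting day-365 outcomes from participants who stop study treatment but still consent

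*Protocol*

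**What the plan says.** Protocol section 7 is the only place that deals with stopping. Its rule is that "Participants may at any time terminate the study if the physician responsible for the study deems it necessary with medical justification". The reasons listed are "allergy to the medicine, safety risk, or other adverse circumstances". It continues: "The participant in question will be informed immediately of health concerns, project termination, and future treatment plan". Withdrawal of consent then follows as a separate route: "Additionally, participants may, at any time, withdraw their informed consent". The physician-led route therefore concerns people who still consent.

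Section 5.1 sets the follow-up that the trial needs for both interventions: "The primary outcome targets admissions and death within 365 days of randomization". The endpoint is "Number of hospitalization-requiring COPD exacerbations and/or death within 365 days".

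Section 6, under documentation and reporting of adverse events, limits the safety window: "Events will be considered exclusively within the trial period, encompassing participant enrollment from screening to the last visit day". SAEs are sought at the 3-monthly follow-ups and by review of the electronic patient file.

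On data sources, section 4.6 says "Data will be obtained via the electronic health record". Section 4.2 allows investigators to read health files for medication and admissions while the project runs.

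Section 5 gives 444 participants, 222 per side of each factor. No dropout allowance is stated beside that figure.

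**The concern.** Stopping a study drug and leaving a study are different events, and section 7 describes only the second. A participant who reacts to azithromycin and leaves may have no recorded admission or death status at day 365. That person belongs to the ICS comparison as much as to the azithromycin comparison, so one exit can take an outcome from both.

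The loss need not be random. Safety risk and adverse circumstances could include deterioration after ICS is stopped. If such people leave the guided arm before an admission that would have counted, the observed risk in that arm falls and the two arms look more alike. In a non-inferiority comparison this favours the claim under test.

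For azithromycin, later SAEs in people with a suspected reaction would have no stated collection route. An analysis plan can say how missing outcomes are handled, but it cannot recover outcomes that were never collected. That makes this a matter for the protocol.

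**Working it through.** **1. The passages side by side.**

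| Question | Protocol |
|---|---|
| What happens on allergy, safety risk or other adverse circumstances? | Study termination at the physician's judgement (section 7) |
| Is there an off-treatment, on-study status? | None stated |
| Is this consent withdrawal? | No, that is listed separately (section 7) |
| How long are primary outcomes needed? | 365 days from randomisation (section 5.1) |
| How long do adverse events count? | To the last visit day (section 6) |
| Is collection after termination described? | No. Sections 4.2 and 4.6 make it feasible but do not provide for it |

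**2. The plan's own figure.** The protocol gives no termination rate, so there is none to reproduce. The related figure is 222 per side at one-sided 2.5% and 80% power.
- ICS, 30% in both arms, margin 0.11: n = 2 × 0.30 × 0.70 × (1.960 + 0.842)² / 0.11² = 273 per side (546).
- Azithromycin, 30% v 20%, pooled variance: n = (1.960 × √(2 × 0.25 × 0.75) + 0.842 × √(0.21 + 0.16))² / 0.10² = 294 per side (588).

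The stated 222 is not reproduced. At 222 per side, power is 71.5% for ICS and 68.3% for azithromycin. That is a separate matter and this point does not depend on it. It matters here only because there is no reserve: losing an assumed 5% of outcomes gives 69.3% and 66.1%, and losing 10% gives 67.0% and 63.7%.

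**3. Possible bias in the ICS comparison.** From section 5: control risk 0.30, guided-arm risk at the limit 0.41, 222 per side, one-sided 2.5%. Assumed: 11 guided-arm participants (11/222 = 5%) leave before any event, none leave control, and leavers drop out of both numerator and denominator. Let r be the risk that a leaver would have had an event by day 365.

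- Guided-arm risk observed: p = (0.41 × 222 − 11r) / 211
- SE = √(p(1 − p)/211 + 0.30 × 0.70/222)
- P(declare non-inferiority) = Φ((0.11 − (p − 0.30))/SE − 1.96)

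| r | p | Difference | SE | False non-inferiority |
|---|---|---|---|---|
| 0.41 (arm average) | 0.4100 | 0.1100 | 0.0457 | 2.5% |
| 0.50 | 0.4053 | 0.1053 | 0.0457 | 3.2% |
| 0.60 | 0.4001 | 0.1001 | 0.0457 | 4.1% |
| 0.75 | 0.3923 | 0.0923 | 0.0456 | 5.8% |
| 1.00 | 0.3792 | 0.0792 | 0.0454 | 10.0% |

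**4. Equal loss in both arms.** If 11 who would have had an event leave each arm, control becomes (66.6 − 11)/211 = 0.2635 and guided stays at 0.3792. The difference is 0.1157, SE 0.0451, and the false non-inferiority rate is 1.8%, below nominal.

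**5. Dependence on how leavers are counted.** Suppose the 11 stay in the denominator as event-free. With r = 1, p = (91.02 − 11)/222 = 0.3605 and the rate is 19.8%. How leavers are counted may be set in the analysis plan. Collecting the outcome removes the question.

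**The case against.** The strongest reply is that section 7 is permissive. It says a participant may leave if the physician finds it necessary. It does not require exit after a drug reaction, forbid staying on study off treatment, or state that outcome collection ends. This stands. A reader might infer that every reaction removes the participant and that follow-up then stops; the text does not say so.

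A second reply is that the last-visit limit belongs to adverse event reporting. The primary endpoint has its own 365-day window with no exception for those who stop, and file access is not tied to each participant's last visit. This also stands, so the safety window cannot be read as cutting off the primary endpoint. What remains is that nothing tells a site to keep collecting after a participant has been told that the project has ended for them. Practice is left to each site.

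A third reply is that the bias is hypothetical. Safety risk is not defined as worsening after ICS is stopped, a worsening that prompts exit may itself be an admission that already counts, and no exit rate is given. This stands as a limit on size. The direction still follows if guided-arm leavers are at higher risk and control has no matching loss.

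A reader might also ask for a safety period after month 12. The protocol gives a risk-based rationale for its safety reporting on marketed drugs, and such a period would not touch either primary comparison. It is a preference and is not part of this point.

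**Conclusion.** The point holds as a gap in the protocol. The only stated action for a treatment-related problem is to leave the study, and no route is given for collecting day-365 admissions, death or SAEs from a still-consenting participant who does so. Both primary comparisons can lose the outcome, and the sample size shows no allowance for it.

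The size is unknown. With 11 of 222 lost from the guided arm only and dropped from the count, the false non-inferiority rate runs from 2.5% at average risk, through about 4% (risk 60%) and about 6% (risk 75%), to 10% if every leaver would have had an event. Equal numbers lost at equal risk in both arms do not inflate it. The number leaving, their risk and the one-sided loss are all assumptions. It would be tempting to quote the 10% figure alone, but the documents do not support the extreme case behind it.

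This should be fixed. It does not show that either primary result will be biased.

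**What to change.** In section 7, separate two things: stopping azithromycin/placebo or leaving the assigned ICS strategy, and withdrawing consent. State that the former does not end participation. Admissions, death and SAEs are then collected to day 365, through the 3-monthly contacts or electronic-file review, unless consent to that collection is withdrawn.

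In section 6, state that for such participants the event window runs to day 365, so that it agrees with section 5.1.

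Leave the clinical decision to stop treatment unchanged. Analysis sets and the handling of any outcomes still missing can stay with the statistical analysis plan.

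The cost is a short protocol amendment and a file review for each early stopper. The planned end of data collection need not move on this account: day 365 for a participant included on 31AUG2025 is 31AUG2026.

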8.1 Remuneration

Participants will not receive remuneration for project participation, but the cost of Azithromycin/placebo treatment during the trial period will be covered by the sponsor.

9. Publications of Trial Results

The trial is a part of a PhD thesis. The results from the trial will be published regardless of whether they are positive, negative, or inconclusive. The trial will be registered and published at clinicaltrials.gov, clinicaltrialsregister.eu as well as published in an international peer-reviewed scientific journal and in The Journal of the Danish Medical Association. At least one publication in a high impact scientific journal is expected. If publication in a scientific journal is not possible, the results will be published as an online report. In addition, a summary of the results will be submitted

to the CTIS and the Clinical Trials database (www.clinicaltrials.gov) as soon as possible and no later than one year after the trial has ended.

10. Scientific Perspective

AECOPD are often accompanied by markedly reduced lung function and increased likelihood of progression of COPD and mortality. In many cases, the illness progression following an exacerbation is irreversible. Therefore, the everyday life of COPD patients is often characterized by fear and anxiety of these acute exacerbations. In addition to the risk of exacerbations, the risk of side effects from the medical treatment of COPD often creates additional concerns for COPD patients. Corticosteroids in the dosages given both for maintenance and for AECOPD carry high risks for the patient: dysregulation of glucose hemostasis (17), high risk of pneumonia and other infections (23, 24), and emergence or worsening of osteoporosis and the consequent fractures (8). Such side effects can lead to a vicious cycle of anxiety, physical deconditioning, muscle wasting, loss of social life, increased risk of further AECOPD, more corticosteroids, and again more side effects. We believe that this trial has the potential to impact the current COPD guidelines seeing that it can provide relevant information for the development of a treatment plan that has the potential to reduce the usage of ICS by 80%⁸, minimize ICS-induced complications and increase the patients' quality of life.

As for Azithromycin, little is known about the mechanism of its effect. Only one large, randomized trial has been performed patients with severe COPD (50% had an exacerbation in the previous year) (22). We aim to determine how prophylactic long-term Azithromycin treatment alters airway inflammation and the respiratory microbiota, and whether Azithromycin can reduce exacerbation rates in COPD patients with GOLD class E and/or FEV₁ < 30%.

⁸ 20% of COPD patients in class C/D have blood eosinophil counts $\geq 0,3 \times 10^9$ cells/L.

We recognize the importance of understanding individual differences in clinical response, biological information, and microbiota changes in response to combined medication. We hope to provide an in-depth understanding of key biological and physiological mechanisms that lead to AECOPD with this study. With a better understanding of the interplay between microbiota changes and therapeutic influences on this by ICS and Azithromycin, the treatment of COPD symptoms can be continuously reevaluated and adapted to each patient.

11. Research Ethical Statement

The research project will be carried out in accordance with the Helsinki Declaration, the Danish Data Protection Act, the Danish Health Act, and the General Data Protection Regulation (EU) 2016/679 (GDPR).

The study is approved through the CTIS and will be conducted in compliance the Clinical Trials Regulation (EU) No 536/2014 (CTR) and with the principles of good clinical practice, as this statement a requirement under the CTR.

The study will be registered in the US Clinical Trials database (www.clinicaltrials.gov), which is based on guidelines defined by The Food and Drug Administration.

Since study participants will not be exposed to irresponsible risks and can greatly benefit from the study's results and participation in the study, we believe that the study is scientifically and ethically sound.

12. Informed Consent

Participation in the trial is voluntary, and participants will not receive any form of financial compensation for participation. . Participants are protected under the Personal Data Processing Act, and the study is reported to the Regional Science Ethics Committee (VEK), the Danish Medicines Agency (Lægemiddelstyrelsen), and the Danish Data Protection Agency (Videnscenter for Dataanmeldelser).

13. Compensation and Reimbursement Schemes

The trial is covered by the patient compensation scheme. Participants can apply for compensation in accordance with Statutory Order No. 1113 of 7 November 2011 on the right of appeal and compensation in the healthcare system if participants experience unexpected damage during the trial or at inclusion.

14. Authorship Criteria

This study investigates two interventions: Eosinophil-guided administration of inhaled corticosteroids treatment regimen and prophylactic treatment with low dose Azithromycin

respectively. Both interventions are planned to result in one main publication each. In addition to these, the microbiota sub-study is also planned to result in a main publication.

In addition to the main publications a number of secondary publications are planned, but are not further dealt with in this section.

Authorships to one of the main publications are granted to a person who have made a substantive contribution. A substantive contribution includes one or more of the following:

- design or conceptualization of the study⁹, or
- major role in the acquisition of data¹⁰, or
- analysis or interpretation of the data¹¹, or
- drafting or revising the manuscript¹².

All authors approve the final version to be published.

⁹ Protocol drafting and major protocol revising along application for national ethics committee and national health authority approval.

¹⁰ Inclusion of 10 patients at a centre is considered a major role in the acquisition of data and entitles one authorship for every 10 patients included at the same centre. It is the responsibility of the primary investigators at each centre, that authorship(s) at the centre are granted to the contributing investigator(s). Also, coordinating across centres (coordinating investigator) is considered a major role in the acquisition of data and entitles one authorship.

¹¹ Data analysis and interpretation are conducted by DMSB, sponsor, coordinating investigator and the writing group.

¹² The writing group is constituted after data acquisition has been completed, but will at a minimum consist of the sponsor, coordinating investigator and primary investigators of sites which have recruited a minimum of 10 patients.

15. References

